This study will be implemented 2 primary health care units (PHCUs), comprised of one health center and all kebeles/health posts in their catchment area, in Hitosa Woreda and 2 PHCUs in Lude-Hitosa Woreda. We randomly assigned 1 PHCU in each Woreda to the intervention and control arms. So out of 4 PHCUs in each Woreda, 1 was selected for intervention and 1 for control.

We obtained the total population for each PHCU. To estimate the number of women age 15-49 and expected pregnancies at the time of study survey, we used results from the Ethiopia mini DHS 2014: 43.6% of female residents of selected households were age 15-49 and 7.3% of women age 15-49 were currently pregnant at the time of the Mini DHS 2014.

Table 3: Estimation of eligible population

Arm	Total population	Female population (50%)	Expected females age 15-49 (43.6% of female pop)	Expected current pregnancies (7.3% of women 15-49)	Women 6-9 months pregnant (pregnancies / 3)
Intervention	72,138	36,069	15,726	1148	382
Comparison	52,508	26,254	11,446	835	278

For pregnant women, we calculated the minimum sample size requirements for this quasi-experimental design for the main outcome of interests (adoption of LAM and other modern method by 12-month PP) using the formula:

$$n' = \frac{\{z_{1-\alpha/2}\sqrt{2\bar{p}(1-\bar{p})} + z_{1-\beta}\sqrt{p_1(1-p_1) + p_2(1-p_2)}\}^2 (1 + (m-1)\rho)}{(p_1 - p_2)^2}$$

where, $p = (p_1 + p_2) / 2$

Where p_1 and p_2 are the proportions of women adopting LAM or other modern method in the intervention and control arms, respectively, and Z's are the critical value of the normal distribution at $\alpha=0.05$ and $\beta=0.20$; $1+(m-1)\rho$ captures the design-effect due to cluster based sampling of areas, where m = average size of the clusters and ρ =intra-cluster correlation. We consider a design-effect (deff) of 1.5 for adjusting higher intra-cluster correlation in the observations in the quasi-experimental design.

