We require a minimum of 299 women in postpartum observation period in each arm to detect an increase of at least 10% contraceptive prevalence rate (CPR) in the intervention arm, compared to the women in the control arm (20% vs 10% in the intervention and control arm, respectively) with $deff=1.5$ at 80% statistical power. Assuming about 20% lost-to-follow-up and non-response rate, we target to enroll 375 women in each arm. We consider that it will be sufficient to select 1 PHCU and its attached *kebeles* in each of the two *woredas* to ensure adequate sample size, with 2 PHCU randomly assigned to the intervention area (1 per *woreda*) and 2 to the control area (1 per *woreda*). The eligible women in 3rd trimester who consent to participate in the study voluntarily will be recruited and be interviewed at enrollment and at 12-month PP.

We used $p_1=0.2$ (20% PP contraceptive uptake by the final round of observation in the intervention arm) and $p_2=0.1$ (10% in the comparison arm). We considered $deff=(1+[m-1]\rho)= 1.5$. Because we are targeting 375 sample size of pregnant women in each arm consisting of 2 PHCUs, this implies $m=188$ AND $\rho=0.0027$.

Because the selected PHCUs are adjoining *woredas* of the same zone, it is expected that they will be quite similar, and in addition, the underlying population are all similar in terms of postpartum status; hence ρ very small (the larger the heterogeneity, the larger the ρ value). The Ethiopia DHS 2011 results suggest that the $deff$ of contraceptive use in all 11 regions are much smaller than the national level $deff$ of CPR (Appendix B – Estimates of Sampling Errors); *woreda* level $deff$ is expected to be much smaller due to less heterogeneity at *woreda* level, compared to the region/state level. In all regions, method specific $deff$ was <1.5 . So, we considered that of $deff=1.5$ is applied in this study is reasonable and practical. A study on postpartum use of contraceptive method at a *woreda* level in Ethiopia also had $deff=1.5$ (Abera Y, Mengesha ZB, Tessema GA. Postpartum contraceptive use in Gondar town, Northwest Ethiopia: a community based cross-sectional study. BMC Women's Health. 2015;15:19.)

Sample size requirements are included below based on the average number of providers and HDAs and managers in each *kebele*. See Table 4: Sample Size Summary

Table 4: Sample Size Summary

Study Participant	Intervention (2 PHCU)	Comparison (2 PHCU)	Total
Pregnant women	375	375	750

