#### A. Quantitative interviews with Women:

After data have been thoroughly examined for quality, the study team will perform exploratory data analysis of key variables such as checking frequency distributions, measures of variability, central tendency, and data outliers. We will also check for incomplete data and consider strategies to handle missing values such as undertaking an imputation strategy and weighting adjustments for non-responses.

We will compare differences by study arm for key variables. Analysis will account for clustering of variables at kebele (village) level using the Taylor linearization method. Differences between the arms for categorical variables will be assessed using the Pearson chi-squared test with the Rao-Scott correction. Differences in continuous variables will be assessed using an adjusted t-test. In case of substantial differences between the study arms, we will perform propensity score matching and perform the analysis with inverse probability weights.

Key descriptive variables:

- Sociodemographic data such as age, marital status, education, and socioeconomic status (nationally representative SES will be determined using the EquityTool described here: <http://www.equitytool.org/>)
- (Baseline only) Proportion of pregnant women with non-first pregnancies (non-primiparous) who previously used family planning
- Number of health system contacts where FP was discussed or provided, by type of contact (ANC, PNC, immunization, etc) and provider (facility provider, HEW, volunteer)
- Proportion of postpartum women who chose a method prior to delivery, by method, and received chosen method
- Proportion of postpartum women who used FP during the first 12 months after giving birth, by method
- Reasons for starting and stopping contraceptive methods and duration of use

- Initiation and duration of exclusive breastfeeding and lactational amenorrhea (LAM); average/median duration of postpartum amenorrhea, PP sexual initiation/PP abstinence
- Partner communication about family planning

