We will fit multivariable logistic regression models for the primary and secondary binary outcomes (see below) to examine differences between the study arms, adjusted for confounding covariates and clustering at kebele level. We will also conduct a “per-protocol analysis” by examining the “dose-effect” of health system contacts on the primary and secondary outcomes, regardless of study arm. We will run two dose-effect models, looking at the association between the outcomes and 1) the total number of contacts and 2) the number of contacts during which FP was discussed as reported by the woman. For the secondary outcome, we will only include contacts during pregnancy since contacts after the birth would not have a temporal effect on whether the woman chose a method prior to delivery.

- Primary outcome:
  - Proportion of interviewed postpartum women who used a modern family planning method within 12 months after giving birth
- Secondary outcome:
  - Proportion of interviewed postpartum women who chose a method prior to delivery

We will also conduct time-to-event analyses using life-table method and use a log-rank test to test for differences in survival distributions between the study arms in terms of the timing of FP uptake after birth. We will perform multivariable hazards model (Cox’s proportional model or parametric model with Weibull distribution in case of non-normality in hazards function) for adjusting confounding covariates and clustering effects.

Additionally, we will run hazards regression models for women who initiated exclusive breastfeeding/LAM after birth to test for differences between arms in the duration of exclusive breastfeeding/LAM use.

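### The SAP states no clustering adjustment for the log-rank test of uptake timing; run as an ordinary test, its false-positive rate would be about 10–11% at the protocol's PHCU-level design effect

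*SAP*

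**What the plan says.** SAP section A (Quantitative interviews with Women) sets out the arm comparisons on the women's data:

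- A general sentence, in the paragraph on comparing key variables by arm, says the analysis will allow for kebele-level clustering by Taylor linearization. Two corrected tests follow: "Differences between the arms for categorical variables will be assessed using the Pearson chi-squared test with the Rao-Scott correction", and an adjusted t-test for continuous variables.
- The primary outcome (modern method used within 12 months of birth) and the secondary outcome (method chosen before delivery) are binary. Both get logistic models adjusted for covariates and kebele clustering.
- For the timing of uptake, the SAP plans life tables and will "use a log-rank test to test for differences in survival distributions between the study arms". No clustering adjustment is named. The next sentence brings in a Cox or Weibull model and gives that model the task of handling covariates and clustering.

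Protocol section III.B sizes the study with a design effect of 1.5, tied to 188 women per PHCU and an intra-cluster correlation (rho) of 0.0027, and concludes: "We require a minimum of 299 women in postpartum observation period in each arm". The PHCU is the unit of assignment, with two per arm. The protocol's own data analysis plan (section V) lists a hazards regression for uptake timing and no log-rank test.

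**The concern.** An ordinary log-rank test takes its variance as if all women were independent. The protocol does not assume independence: it raises the required sample by half to allow for clustering. An analyst who follows the time-to-event paragraph as written would most naturally run the ordinary test and leave clustering to the model in the next sentence.

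The report would then carry two arm tests on one endpoint, one of them possibly anti-conservative, and the SAP has no rule on which governs. Uptake through 12 months is the subject of the SAP's first objective, so a small log-rank p-value could be read as support for the intervention when the adjusted model gives none.

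**Working it through.** **Inputs.** From protocol III.B: two-sided alpha 0.05, power 80%, uptake 20% against 10%, design effect (deff) 1.5, m = 188 women per PHCU, rho = 0.0027, 299 women analysed and 375 enrolled per arm, two PHCUs per arm. From Table 4: 10 health posts in the intervention clusters and 8 in the comparison clusters.

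**1. The protocol's figures reproduce.**

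- With pooled proportion 0.15, n = [1.96 × √(2 × 0.15 × 0.85) + 0.8416 × √(0.2 × 0.8 + 0.1 × 0.9)]² / 0.1² = 198.96.
- 198.96 × 1.5 = 298.4, which rounds up to the stated 299.
- 299 / 0.80 = 373.75, or 374, against the stated 375.
- rho = (1.5 − 1) / (188 − 1) = 0.00267, which rounds to the stated 0.0027.

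**2. Size of an unadjusted test.** If the true variance is deff times the assumed variance, a nominal two-sided 5% test rejects under the null with probability 2 × [1 − Φ(1.96 / √deff)]. At deff 1.5, 1.96 / 1.2247 = 1.600, which gives 0.1095. A true 5% test would need |z| above 1.96 × 1.2247 = 2.40 (chi-squared 5.76), in place of 1.96 (3.84).

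**3. How the result depends on the cluster assumed.** Here deff = 1 + (m − 1) × rho, with rho = 0.0027 below the first row.

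| Clustering counted | m | deff | False-positive rate |
|---|---|---|---|
| PHCU, protocol's planning value | 188 | 1.50 | 11.0% |
| PHCU, analysed women (299 / 2) | 149.5 | 1.40 | 9.8% |
| Kebele, largest (375 / 8) | 46.9 | 1.12 | 6.4% |
| Kebele, smallest (299 / 10) | 29.9 | 1.08 | 5.9% |

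The kebele rows rest on two assumptions: one health post per kebele, so 8 to 10 kebeles per arm, and the PHCU-level rho holding at kebele level. The documents give neither a kebele-level rho nor a count of women per kebele. Adding kebeles from adjoining PHCUs, as III.B allows, would lower the women per kebele.

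**4. Does a formula for a general z-test carry over to the log-rank test?** Log-rank tests were simulated with no arm effect, two PHCUs per arm, monthly times to 12 months, rho = 0.5 / 187, and assumed 12-month uptake of 10% to 50%. The rejection rate was 10.7–11.4% at m = 188 and 9.7–10.2% at m = 150. With no clustering it was 4.7–5.5%. The formula therefore describes this test well.

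**The case against.** The strongest reply is that the general clustering sentence sits in the same SAP section and can be read to cover every arm comparison there. Silence in one sentence proves little: the dose-effect models and the breastfeeding/LAM hazards models carry no clustering wording either. This part stands. A reader might infer that the SAP deliberately specifies an unadjusted test, and the documents do not support that. What they show is that no adjustment is stated. The general sentence still does not settle the matter. It belongs to the comparison of key variables, it is followed by corrected versions of two tests only, and it does not say what a clustered log-rank test would be. The SAP also restates clustering for the logistic models and for the hazards model on uptake timing.

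It can also be said that inference on this endpoint is already protected by the clustered hazards model. That stands too, and it limits the exposure to a supporting test. It does not stop the log-rank p-value from being reported and cited.

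Finally, 1.5 is a planning value that the protocol presents as ample, since it expects a much smaller design effect at woreda level. That stands as a caution: 11% is conditional on that value and is not a property of the test. A reader might go the other way and extend the formula to design effects of 2 or 3 (16.6% and 25.8%). Neither document supports values that high for this study.

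**Conclusion.** The gap is real and confined. If the log-rank test is run in its ordinary form, its two-sided false-positive rate is about 10–11% at the protocol's PHCU-level design effect: 11.0% at 1.5, and 9.8% at 1.40 with 299 analysed women per arm. It is about 6% if only kebele clustering at the same rho is counted, assuming 30 to 47 women per kebele. The lower figure leaves out correlation within PHCUs, which are the assigned units and the level at which the protocol derived its design effect.

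A reader might infer that the study's main conclusion is at risk from this test. The documents do not support that: the primary and secondary outcomes are binary and have cluster-adjusted models, and uptake timing has a cluster-adjusted hazards model. The point should be corrected before analysis, as a matter of one supporting p-value.

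**What to change.** In SAP section A:

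- Present the life-table curves by arm descriptively.
- Take the arm test for uptake timing from the clustering-adjusted hazards model, by a robust score or Wald test with arm as the only term, and report it beside the planned covariate-adjusted model. Naming a cluster-adjusted log-rank test instead is equally acceptable.
- If an ordinary log-rank p-value is still shown, label it descriptive and do not use it for inference.
- State the cluster unit, and state that a kebele-level adjustment does not by itself cover correlation within PHCUs. The change makes this test consistent with the primary analysis but does not guarantee an exact 5% size.

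The cost is a few lines of SAP wording and a p-value that will be less favourable. No new data are needed. Because the protocol lists only a hazards regression for uptake timing, making the log-rank test descriptive drops nothing the protocol promised.

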Inter-pregnancy intervals of less than 24 months are associated with higher rates of newborn and child mortality, as well as higher probability of pre-term and low birth weight newborns, and malnutrition and stunting among children under five (Kozuki et al, 2013; Cleland 2012). An MCHIP secondary analysis of the 2011 Ethiopia DHS (MCHIP 2013) revealed that among all non-first births, 47% of pregnancies occur at less than the 24 month inter-pregnancy interval (13% of women are pregnant before the end of the first year postpartum). Looking at prospective unmet need (defined as whether women would like another child within the next two years), among Ethiopian women 0-2 years postpartum ($n = 4,453$), 94% of women did not wish another pregnancy at the time of the survey yet only 19% used a modern method of contraception, resulting in a prospective unmet need among postpartum women of 74%. This compares to an unmet need of 34% among postpartum women using the standard DHS method of calculating unmet need which uses a question about the desire for the recently born child for the subset of postpartum women in the total sample (Moore et al, 2015).

Exclusive or predominant breastfeeding offers protection against rapid fertility return during the first 6 months after childbirth; however, rates of exclusive and predominant breastfeeding drop off rapidly in Ethiopia starting in the second month of life. While 70% of newborns (0-1 month) are exclusively breastfed, only 32% of infants 4-5 months old are exclusively breastfed. Only 4% of children 6-23 months are fed appropriately based on infant and young child nutrition (IYCN) recommendations and 44% of children less than 5 years of age are stunted (DHS 2011).

Women in Ethiopia do not access formal health services as frequently as they should. Only 43% access any antenatal care services and 19% are seen for at least 4 ANC visits during pregnancy, with wide differences between urban and rural women. The majority of births (89.5%) still occur at home, are not attended (3.8%) or attended by a traditional birth attendant (TBA) (28.4%) or relative (56.6%). Only 6.7% of mothers and babies had a postnatal check within two days of birth. Vaccination coverage is higher with BCG at 79.6%, DPT-HepB-Hib1 at 80.0%, DPT-HepB-Hib3 at 65.7%, OPV1 at 90.1%, OPV3 at 70.5%, and measles at 68.2% (Ethiopia NICS 2012), though it falls short of international recommendations of country coverage of over 90%.

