More robust qualitative evaluation will take place at endline, where secondary participants will include community health workers (HDAs), and facility based providers, including HEWs, and managers. We will collect additional data from these informants through interviews, questionnaires and focus group discussions.

The following conceptual model illustrates the inputs and influencers that affect postpartum family planning uptake and how tracking pregnant women will improve the uptake.

Figure 2: Conceptual Model

The study will collect data from key actors in the implementation of the intervention. The Table 1 describes the actors, the type of data and instruments to be collected.

Table 1: Data Collection Tools and Type of Information Collected		
Study Population	Data Collection Method	Type of Information/Data Collected
Health Extension Workers	Mixed methods questionnaire (going through each point of service – ANC, delivery, PNC and immunization)	
 • Integration of PFPF messages in ANC, PNC, and immunization contacts • Perceived barriers to uptake of PFPF in community • Experience with training, mentoring and supervision of HDA in promoting PFPF • Confidence (self-perceived skills and ability) and experience in counseling and delivering postpartum implants, LAM counseling & EBF support, and other methods • Ability and willingness to use record keeping and tracking tools to assess population level PFPF decision-making and uptake in the catchment of the health post
Health Development Army (HDA)/HDA team leaders	Focus Group Discussions	
 • Understanding of PFPF benefits, methods, etc. • Experience promoting MNCH including PFPF • Description of what they do and how (home visits, community meetings, etc.) • Decision making as to who they target besides pregnant women, barriers perceived, coverage of assigned households • Experience with support from HEWs, team leaders, village leaders, use of data at monthly meetings

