Study Population	Main Data Collection Method	Other Study Procedures	Number of contacts	Duration of Research Interview (Only)	Place of Interview
	Review Client held Integrated MCH/Family Health Card (post intervention)				
Registers, Referrals at Health Center, Health post level	(Revised longitudinal register) For HEW monitoring tool: Ease of use, helpful for data review meetings, etc		12: monthly data review and abstraction	N/A	Health Post and Health Center

4. Provide a brief data analysis plan and a description of variables to be derived.

After data have been thoroughly examined for quality, the study team will perform exploratory data analysis of the key variables for checking frequency distributions, measures of variability, central tendency, and data outliers. We will also check for incomplete data and undertake an imputation strategy, if needed.

We will examine the differences in contraceptive use behavior by study arms for the following outcomes:

- Baseline only: % with past use of postpartum family planning among women with non-first pregnancies
- % of postpartum women who choose a method prior to delivery (by # of ANC contacts)
- % uptake of FP by PP timing (Delivery, PNC, immunization) and type of method
- % of ANC and PNC contacts where FP was discussed or provided (by type of contact, i.e., HDA, HEW, HCW, other)
- Duration of exclusive breastfeeding/Introduction of complementary foods
- % initiated LAM and the duration of LAM use
- % of women received counseling during immunization
- Immunization coverage of infants of enrolled women by month postpartum (doses of DPT1, 2 and 3 and drop out rates)

We will perform both “intent to analysis” to examine the net differences between the two study arms, adjusted for confounding covariates, and “per-protocol analysis” to examine “dose-effect” of health system contacts. We will fit multivariable logistic regression models for examining the differences in binary outcome variables (e.g., method selection during ANC; FP discussions during contacts, etc). We will use hazards regression model for examining the duration (discontinuation) of LAM use in first 6-month PP and for analyzing the uptake of modern contraceptive method by timing since delivery.

1. Describe whether you are collecting or storing personal identifiers, and if yes, why you need them, and when and how you plan to dispose of them. Signatures on consent forms are considered to be identifiers.

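### The between-arm test of exclusive breastfeeding/LAM duration is restricted to women who started, an event after allocation that the intervention may change, so selection can bias the hazard ratio

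*SAP*

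**What the plan says.** The last paragraph of SAP section A plans this analysis: "we will run hazards regression models for women who initiated exclusive breastfeeding/LAM after birth to test for differences between arms in the duration". It is a test between arms, and its analysis set is defined by something that happens after birth. The protocol's brief data analysis plan (section V.C, item 4) has a related analysis, a "hazards regression model for examining the duration (discontinuation) of LAM use in first 6-month PP", and does not state its denominator.

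Elsewhere the documents treat initiation as something that may differ by arm:

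- The same protocol item lists, among outcomes to be examined by arm, the percentage who "initiated LAM and the duration of LAM use".
- The sample-size text (protocol III.B) defines the main outcome as "adoption of LAM and other modern method by 12-month PP" and plans for "20% vs 10% in the intervention and control arm, respectively".
- Table 1 of the protocol includes "LAM counseling & EBF support" among the topics on which health extension workers are to be questioned.

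SAP section A also lists initiation and duration of exclusive breastfeeding and LAM among the descriptive variables. It allows propensity-score weighting if the study arms differ substantially.

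**The concern.** Allocation makes the arms comparable, as far as it can with two primary health care units per arm, for all enrolled women. It gives no such assurance for women who went on to start exclusive breastfeeding or LAM. If counselling persuades women who would not otherwise have started, the intervention arm's initiators contain a subgroup with no counterpart among the control arm's initiators. If that subgroup tends to stop sooner, it raises the intervention arm's stopping rate even though nobody's duration was shortened.

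The SAP has no step that deals with this. The weighting step is conditional and directed at differences between the study arms, not at selection into the initiator group. Covariate adjustment helps only as far as measured covariates explain who is persuaded to start and how long they continue. No all-women model of duration is specified. At stake is the reading of the breastfeeding/LAM result: an intervention that adds months of exclusive breastfeeding or LAM could be reported as hastening discontinuation.

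**Working it through.** **The plan's own figure.** The documents give no figure for the duration analysis. The stated minimum of 299 women per arm, used below for precision, reproduces from the protocol's formula: {1.96·√(2×0.15×0.85) + 0.8416·√(0.16+0.09)}² / 0.10² = 198.96. Multiplied by the design effect of 1.5 this is 298.4, so 299.

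**Inputs.** Neither initiation by arm nor duration is given, so these are assumptions: exponential durations, follow-up to 6 months, a mean of 5 months for women who would start in either arm (usual initiators) and 2 months for women who start only because of the intervention (extra initiators). Initiation of 70% is used only as a scale for exclusive breastfeeding. It comes from the Background: "While 70% of newborns (0-1 month) are exclusively breastfed, only 32% of infants 4-5 months old are exclusively breastfed". That is status at 0-1 month. It is neither initiation nor LAM. LAM at 20% versus 40% is an assumed doubling.

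**Formulas.** Restricted mean to 6 months for mean duration m: R(m) = m(1 − e^(−6/m)). This gives R(5) = 3.494, R(2) = 1.900 and R(6) = 3.793. With initiation p_c and p_i and w = p_c/p_i:

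- initiators: control R(5); intervention w·R(5) + (1−w)·R(2);
- all women, non-initiators at zero: p_c or p_i times the initiator value.

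The hazard ratio e^b is the large-sample Cox value. It solves ∫₀⁶ [p_i f_i(1−π) − p_c f_c π] dt = 0, with π = p_i S_i e^b / (p_i S_i e^b + p_c S_c).

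**Example, 70% versus 85%.** w = 0.70/0.85 = 0.8235. Intervention initiators: 0.8235×3.494 + 0.1765×1.900 = 3.21 months, against 3.49. All women: 0.85×3.21 = 2.73, against 0.70×3.494 = 2.45.

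| Initiating, control vs intervention | Effect on usual initiators | Initiators, months | All women, months | HR for stopping |
|---|---|---|---|---|
| 70% vs 75% | none | 3.49 vs 3.39 | 2.45 vs 2.54 | 1.06 |
| 70% vs 80% | none | 3.49 vs 3.29 | 2.45 vs 2.64 | 1.11 |
| 70% vs 85% | none | 3.49 vs 3.21 | 2.45 vs 2.73 | about 1.15 |
| 70% vs 85% | 20% longer (mean 6) | 3.49 vs 3.46 | 2.45 vs 2.94 | about 1.0 |
| 20% vs 40% | none | 3.49 vs 2.70 | 0.70 vs 1.08 | about 1.5 |
| 20% vs 40% | 20% longer (mean 6) | 3.49 vs 2.85 | 0.70 vs 1.14 | about 1.4 |

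If extra initiators also average 5 months and nothing else changes, the hazard ratio is 1.00 in every row. The initiator-only result depends only on the ratio of initiation rates, so 10% versus 20% gives the same 1.5.

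**Against the study's precision.** Use 299 women per arm, the plan's design effect of 1.5 (set for another outcome) and SE(b) = √(1.5/[d·a(1−a)]), where d is the number of stopping events and a the intervention share of initiators.

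- 70% vs 85%: d = 299×(2×0.70×0.699 + 0.15×0.950) = 335 and a = 0.548, so SE = 0.134. The chance of a nominally significant 'harm' is Φ(ln 1.155/0.134 − 1.96), about 19%.
- 20% vs 40%: d = 299×(2×0.20×0.699 + 0.20×0.950) = 140 and a = 2/3, so SE = 0.22. The chance is Φ(ln 1.51/0.22 − 1.96), about 47%. With the 20% lengthening it is about 30%.

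**What an all-women comparison would show, 70% vs 85%, no other effect.** The percentage still exclusively breastfeeding at t months is 0.70e^(−t/5) in control, plus 0.15e^(−t/2) in intervention. This gives 57.3% vs 66.4% at 1 month, 38.4% vs 41.8% at 3 months and 21.1% vs 21.8% at 6 months. The direction is right at each time.

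**The case against.** Several points on the other side stand. Discontinuation is defined only for users, so a model among initiators answers a legitimate question. The protocol uses that term. Initiation is to be reported by arm, so a reader would see a difference beside the hazard ratio, although that does not correct it. The analysis is an additional one, outside the primary and secondary outcomes and the four SAP objectives. The inputs that produce a reversal come from no document. In the exclusive-breastfeeding range the shift is small against the precision: the 95% interval spans a factor of about 1.3 either way.

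A reader might infer that the intervention does change who starts. The documents show this as an aim and a planning assumption, not as a fact. Health centres in both arms receive training in postpartum family planning, so only the community component could shift initiation between arms. A reader might also infer that reversal is to be expected. It needs two conditions, a shift in initiation and earlier stopping among the extra initiators, and no passage establishes the second. Modest lengthening among usual initiators removes the reversal at 70% versus 80% (hazard ratio about 0.95) and brings the hazard ratio to about 1.0 at 70% versus 85%. Finally, 70% at 0-1 month does not mean that 30% of women are available to be persuaded, because some will have started and already stopped.

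**Conclusion.** The point holds as a risk of bias in one planned between-arm test. The SAP conditions on an event after allocation that the plan hopes to influence, and it offers no estimate free of that conditioning. Under the stated assumptions the distortion is mild for exclusive breastfeeding, with a hazard ratio of 1.06 to 1.15 when there is no true effect on usual initiators and about 1.0 when there is a 20% lengthening at 70% versus 85%. It is substantial for LAM if adoption doubles from a low base, about 1.5, or 1.4 with the lengthening. The size rests on the assumed initiation rates, the 5- and 2-month means and the exponential form, and it vanishes if extra initiators last as long as the others. It is worth correcting because the remedy is cheap. It does not touch the primary or secondary outcome.

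**What to change.** In the last paragraph of SAP section A, treat exclusive breastfeeding and LAM separately. For each, make the between-arm comparison in all interviewed women with a live birth, as the percentage still exclusively breastfeeding or using LAM at 1, 3 and 6 months. Restricted mean months to 6 with non-initiators at zero is an alternative. Do not put non-initiators into a hazards model, which would create events at time zero. Adjust for covariates and kebele clustering as in the other models. Keep the initiator-only hazards model, label it descriptive, and print it beside the percentage initiating in each arm.

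The cost is SAP wording. Initiation and duration are already planned variables, so no new data are needed. The small downside is that an all-women measure combines starting with continuing, which is why the initiation percentage and the descriptive model should stay beside it.
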